3.9. Handling of Missing Data

3.9.1. Handling of Partial Dates for Adverse Events

When determining the treatment-emergent adverse events (TEAEs), partial adverse event start and/or end dates will be handled as shown in Table 1.

Date	Missing Part	Imputation Rule
	Missing Day	Assign the first day of month unless it is the same month and year of the first dose of study treatment. Otherwise, assign date of first dose of study treatment or adverse event end date (if not missing), whichever is earlier.
Start Date	Missing Day, Month	Assign Jan 01 unless the year is year of first dose of study treatment. Otherwise, assign date of first dose of study treatment or AE end date (if not missing), whichever is earlier.
	Missing Day, Month, Year	Assign the date of first dose of study treatment or AE end date (if not missing), whichever is earlier.
	Missing Day	Assign the last date of the month or death date or data cutoff date (or end of study date), whichever is earliest.
End Date	Missing Day, Month	Assign Dec 31 or death date or data cutoff date (or end of study date), whichever is earliest.
	Missing Day, Month, Year	If ongoing, the end date is missing. Otherwise, assign death date or data cutoff date (or end of study date), whichever is earlier.

Table 1. Imputation Rules for Adverse Event Partial Dates

3.9.2. Handling of Partial Dates for Medications

When determining if a medication is a prior or concomitant medication, partial start and/or end dates will be handled as shown in Table 2.

Date	Missing Part	Imputation Rule
Start Date	Missing Day	Assign the first day of month unless it is the same month and year of the first dose of study treatment. Otherwise, assign date of first dose of study treatment or medication end date (if not missing), whichever is earlier.
	Missing Day, Month	Assign Jan 01 unless the year is year of first dose of study treatment. Otherwise, assign date of first dose of study treatment or medication end date (if not missing), whichever is earlier.
	Missing Day, Month, Year	Assign date of first dose of study treatment or medication end date (if not missing), whichever is earlier.
End Date	Missing Day	Assign the last date of the month or death date or data cutoff date (or end of study date), whichever is earliest.
	Missing Day, Month	Assign Dec 31 or death date or data cutoff date (or end of study date), whichever is earliest.
	Missing Day, Month, Year	If ongoing, the end date is missing. Otherwise, assign death date or data cutoff date (or end of study date), whichever is earlier.

 Table 2. Imputation Rules for Medication Partial Dates

The imputed date will be used to categorize TEAE, prior/concomitant medication. The data listings will report original data instead as the imputed date.

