  - Female patients must be postmenopausal or surgically sterile or, if of childbearing potential and the partner is not vasectomized (6 months minimum), must agree to use a medically acceptable form of contraception from the time of signing the informed consent form (ICF) through at least 60 days following the last administration of study drug. If only the barrier method is used, a double barrier must be employed. Postmenopausal women must have had ≥ 24 months of spontaneous amenorrhea. Surgically sterile women are defined as those who have had a hysterectomy, bilateral ovariectomy, or bilateral tubal ligation. All women of childbearing potential must have a negative pregnancy test result before administration of study drug.
  - Male patients must be biologically incapable of having children (eg, vasectomized) or must agree to use the above forms of birth control for themselves and their partner from the time of signing the ICF through at least 120 days following the last administration of study drug.

- 6. Be fluent in the local language.
- 7. Male or female aged 18 to 70, inclusive, at time of Visit 1.
- 8. Have a HAMD-17 total score  $\geq 21$  at screening and baseline.
- 9. Be willing to discontinue the use of antidepressant drugs (including over-the-counter medications to treat depression [eg, St John's Wort]) at least 5 half-lives (or at least 1 week for herbal or other over-the-counter medications for depression) prior to baseline (Day -1). For fluoxetine, a washout period of at least 3 weeks for ≤ 20 mg/day and at least 4 weeks for > 20 mg/day is required.

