5.1.4. Medical History

System organ class (SOC) and preferred term (PT) of medical history will be coded with MedDRA Version 25.0 or higher. A subject will be counted only once within one SOC and one PT if the subject reported the same SOC and PT multiple times. The summary will be sorted by the frequency of SOCs and PTs in overall total.

Medical history information collected on "Medical History" CRF page will be listed in subject data listing.

5.1.5. **Prior and Concomitant Medications**

All medications will be coded using WHO Drug Dictionary March 2022.

A medication can be classified as either prior or concomitant medication. Prior medication is defined as any medication taken prior to the date of the first study treatment dose. Concomitant medication is defined as any medication taken on or after the date of the first study treatment dose through the end of study.

Prior and concomitant medications will be summarized by Anatomical Therapeutic Chemical (ATC) Classification (2nd level, chemical subgroup [ATC-2]) and preferred name. A subject will only be counted once within each ATC-2 code and within each preferred name. ATC-2 and preferred name will be sorted in descending frequency for the overall number of subjects and then alphabetically for ties.

Prior and concomitant medications will also be presented in data listings.

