The same model in the primary analysis will be used without imputation using the treatment policy strategy per ICH E9(R1) (Polverejan 2023). This analysis will be used to assess the impact of imputing missing values based on the MAR assumption.

3. MMRM with imputation using pattern mixture model

This sensitivity estimator will be using a control-based multiple imputation method (Ratitch 2013). This sensitivity analysis does not rely on the MAR assumption. Data collected after initiation of prohibited medications will not be used unless otherwise specified. Missing data due to all ICEs will be handled per specifications below unless otherwise specified.

In this sensitivity analysis, imputation will be implemented using SAS MI procedure with FCS statement and REGPMM option, as well as MNAR statement with MODELOBS option to identify observations from the placebo arm for deriving the imputation models, ie, assuming all missing data will have a profile that equals the profile of the placebo arm for all time points. The variables to be used in the imputation are region, baseline values, and change from baseline values observed at Weeks 1, 2, 4, and 6.

One hundred fully imputed datasets will be created. The MMRM described in Section 5.4.1.2 will be used for treatment comparisons. Treatment effects (difference in LS means between treatment arms) from these 100 analyses will be combined to generate the final results using Rubin's method with SAS MIANALYZE procedure.

A tipping point analysis for this sensitivity analysis will also be conducted to assess the robustness of the result. The same steps described in the first sensitivity analysis will be followed.

4. Sensitivity Analyses based on RAS

A set of sensitivity analyses listed below will be performed using DGM4-positive patients in RAS. The same MMRM in the primary and sensitivity analyses described above will be carried out with the exclusion of the following fixed effect: treatment by baseline MADRS total score. In other words, the model will include the fixed effects of treatment, visit (categorical covariate), treatment by visit interaction, baseline MADRS total score (continuous covariate), and region.

The following analyses will be performed in this set of sensitivity analyses:

- 1) The primary analysis, as well as the 1st and 2nd sensitivity analyses based on FAS will be repeated using RAS.

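### SAP Table 2 imputes incomplete medication stop dates with no cap at baseline, so a washed-out antidepressant can be classified as concomitant

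*SAP*

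**What the plan says.** Table 2 in SAP 3.9.2 sets dates for deciding whether a medication is prior or concomitant.

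- **Start date, incomplete.** If the known part falls in the month or year of first dose, the rule is to "assign date of first dose of study treatment or medication end date (if not missing), whichever is earlier". A fully missing start is treated the same way. Otherwise the first of the month or 1 January is used. The matching adverse-event row in SAP 3.9.1 reads: "Assign the date of first dose of study treatment or AE end date (if not missing), whichever is earlier".
- **End date, day missing.** "Assign the last date of the month or death date or data cutoff date (or end of study date), whichever is earliest".
- **End date, day and month missing.** "Assign Dec 31 or death date or data cutoff date (or end of study date), whichever is earliest".
- **End date, fully missing.** "If ongoing, the end date is missing. Otherwise, assign death date or data cutoff date (or end of study date), whichever is earlier".

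The end-date rows are the same as those for adverse events. None refers to baseline, first dose or washout. SAP 3.9.2 adds that imputed dates serve to classify treatment-emergent events and prior or concomitant medication, and that listings show the original data.

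SAP 5.1.5 then says: "Prior medication is defined as any medication taken prior to the date of the first study treatment dose". Concomitant means taken on or after that date, through the end of study.

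Protocol 4.1, inclusion criterion 9, requires patients to "Be willing to discontinue the use of antidepressant drugs" at least 5 half-lives before Day -1. The minimum is 1 week for herbal or over-the-counter products, and 3 or 4 weeks for fluoxetine depending on dose.

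**The concern.** For adverse events, resolving an unknown date towards the treatment period is cautious, because it makes the event treatment-emergent. The same logic fits poorly for medications in this trial. Every patient has had at least two antidepressant courses (Protocol 4.1, criterion 3), and antidepressants must be washed out before baseline. Recent stop dates will therefore often fall in the calendar month or year of first dose, where the end-date rows carry them past first dose.

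The result can contradict what the site recorded: a drug noted as stopped before baseline is tabulated as taken on study drug. The concomitant-medication table would then show antidepressant use that did not happen, and the prior-medication table could lose a real course.

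**Working it through.** There is no stated figure to reproduce. The check applies Table 2 literally.

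**Step 1: worked cases.** Illustrative first dose is 20 Jun 2023, so baseline (Day -1) is 19 Jun. End of study is 28 Aug 2023: last dose on Day 42 is first dose + 41 days, and 28 days of follow-up make + 69. No death or earlier cutoff is assumed. In every row the drug truly stopped before first dose and is not ongoing.

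| Recorded start | Recorded stop | Imputed start | Imputed end | Result |
|---|---|---|---|---|
| Jan 2021 | Jun 2023 | 1 Jan 2021 | 30 Jun 2023 | concomitant (wrong) |
| 2021 | 2023 | 1 Jan 2021 | 28 Aug 2023 | concomitant (wrong) |
| 2023 | Jun 2023 | 20 Jun 2023 | 30 Jun 2023 | concomitant, Day 1 start, not prior (wrong) |
| 2023 | 2023 | 20 Jun 2023 | 28 Aug 2023 | concomitant, Day 1 start, not prior (wrong) |
| unknown | unknown | 20 Jun 2023 | 28 Aug 2023 | concomitant, Day 1 start, not prior (wrong) |
| unknown | 5 Jun 2023 | 5 Jun 2023 | 5 Jun 2023 | prior (right) |
| Jan 2021 | May 2023 | 1 Jan 2021 | 31 May 2023 | prior (right) |
| 2021 | 2022 | 1 Jan 2021 | 31 Dec 2022 | prior (right) |

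The error comes from the end-date rows. The start rule adds a false Day 1 start only after the end date has already been pushed past first dose.

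One ambiguity remains. The start rule does not say whether the medication end date it compares is the recorded or the imputed one. If it is the recorded one, an unknown start with a stop in May 2023 gives a start of 20 Jun and an end of 31 May, which is impossible.

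**Step 2: how often an incomplete stop date is misread.** Let *s* be the days from true stop to first dose, with first dose equally likely on each day of a 365-day year (an assumption).

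Month-only stop date: it is misread when stop and first dose share a month. A month of length L has L − s such first-dose days, so for s ≤ 28 the share is (365 − 12s)/365.

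- s = 7: 281/365 = 77%
- s = 14: 197/365 = 54%
- s = 21: 113/365 = 31%
- s = 28: 29/365 = 8%
- s = 35: 0%

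The average number of false on-study days in the misread cases is 12, 9, 5 and 2 for the first four.

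Year-only stop date: the share is (365 − s)/365, giving 98%, 96%, 94% and 92% at 7, 14, 21 and 28 days. A fully missing stop date on a drug that is not ongoing is always misread, because it goes to end of study.

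These shares are conditional on the stop date being incomplete in that way.

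**Step 3: with the cap.** In the five wrong rows the imputed end becomes 18 Jun 2023. The start rule applied to that date gives at latest 18 Jun. All five become prior only, and every share in Step 2 for drugs recorded as stopped before baseline becomes 0%.

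**The case against.** Much of the case against a wider claim stands.

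- **Not every incomplete date is mishandled.** A complete pre-dose stop date keeps the drug prior whatever is missing from the start, and so does a partial stop date in an earlier month or year (reading the start rule on the imputed end).
- **A reader might infer that such a drug counts as prohibited medication.** Protocol 5.3 does bar antidepressants from baseline, and for sensitivity analysis 3 SAP 5.4.1.3 says: "Data collected after initiation of prohibited medications will not be used unless otherwise specified". The RAS pattern-mixture analysis also replaces such data, and SAP 4.4 excludes patients with disallowed drugs for more than half the treatment period. But SAP 3.9.2 gives imputed dates no role in identifying prohibited use. Other routes exist: eCRF recording with notice to the medical monitor where possible (Protocol 5.3), and individual review before database lock (SAP 4.4).
- **A reader might also turn the shares into lost patients or lost MADRS scores.** The documents give no rate of incomplete dates. A drug with a month-only stop and an earlier start initiates nothing on study. Even if imputed dates fed the per-protocol limit, month-only cases would exceed it in 8% at 7 days and 0% from 10 days. Year-only cases would exceed it in 85% to 92% at 7 to 35 days, but only under that unstated link.
- **Sites checking washout need fairly exact recent stop dates.** This probably makes the problem uncommon.
- **Leaning towards concomitant is defensible when timing is truly unknown.** That includes an ongoing drug with an unknown start, which Table 2 dates to Day 1. Rewriting the start rule in general would be a trade-off, since it could hide real on-study starts.

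None of this defends the end-date rows where the record shows that the drug stopped before baseline. There the rule gives a classification known to be false.

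**Conclusion.** The point holds in a narrow form and is minor. The end-date rows of Table 2 misclassify a washed-out drug when its stop date is known only to the first-dose month or year, or is wholly missing and not ongoing. A Day 1 start, and loss from the prior-medication table, follows only if the start is also fully missing or known only to the first-dose month or year.

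The certain effect, when such dates occur, is on the prior and concomitant medication tables. Sensitivity analysis 3, the RAS pattern-mixture analysis and the per-protocol set are affected only if prohibited use is derived from imputed dates, which the SAP does not say. The primary analysis is unaffected, because SAP 5.4.1.2 keeps data collected after prohibited medication starts.

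The percentages rest on first doses spread evenly over the year and on illustrative stop-to-dose intervals. No patient count can be given.

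**What to change.** In Table 2, add one rule. For any medication recorded as stopped before baseline (not ongoing at Visit 3), the imputed end date may be no later than the day before baseline. State that the start rule compares first dose with this capped, imputed end date; this also removes the ambiguity about which end date is meant. Leave the existing rule in place for all other medications.

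The cost is a slightly longer rule and one more programming check, made before unblinding. The CRF is not among the documents, so the team should confirm that stopped-before-baseline status can be derived from it.

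A sentence saying whether prohibited use is identified from imputed dates or by case review would help, but that is a clarification and not part of the correction.

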3.9.3. Handling of Missing Data for MADRS

For MADRS, the total score is set to missing for any patient if 50% or more items are missing at an assessment. If less than 50% of items are missing, the missing items will take the average from the non-missing items. These calculated total scores will not be rounded to whole numbers.

Missing data for the total score of MADRS will be maintained as missing unless specified otherwise.

3.9.4. Handling of Missing Data for Other Efficacy Scales

Missing data for other efficacy scales will be maintained as missing unless specified otherwise.

4. ANALYSIS SETS

4.1. Randomized Analysis Set

The randomized analysis set (RAS) includes all randomized patients in this study. This analysis set will be used for a sensitivity analysis of the primary and key secondary efficacy endpoints for DGM4-positive patients. The RAS population will be analyzed by treatment randomization regardless of the actual treatment received.

4.2. Full Analysis Set

The full analysis set (FAS) includes all randomized patients who took at least one dose of study drug and had a post-randomization efficacy evaluation. The FAS population will be analyzed by treatment randomization regardless of the actual treatment received. The primary and secondary efficacy results of the study will be based on analysis in FAS patients who are DGM4 positive.

4.3. Safety Analysis Set

The safety analysis set (SAF) includes all patients who took at least one dose of study drug. The safety population will be analyzed by the actual treatment received regardless of treatment randomized.

4.4. Per Protocol Analysis Set

The per protocol analysis set (PP) excludes all patients with one of the following violations:

- Violation of major inclusion or exclusion criteria as determined by the sponsor prior to the database lock
- Study treatment compliance at < 80% or > 120%
- Had disallowed medications during > 50% of the treatment period
- Were mis-randomized
- Others which may impact reliable interpretation of the outcome

All patients with the violations above will be reviewed as potential important protocol deviations. The final list of per protocol deviations will be reviewed and finalized on individual cases prior to the database lock and unblinding. Additional information on protocol deviations is provided in Section 5.1.2.

5. STATISTICAL METHODOLOGY

5.1. Population Characteristics

5.1.1. Study Subjects Disposition

The number of subjects in the FAS and SAF will be presented. The percentage of subjects in FAS will be calculated using the number of subjects in the SAF as denominator.

- Number screened
- Number of screen failures: due to DGM4 status vs all other reasons
- Number randomized
- Number and percentage of subjects who had at least one dose of study treatment
- Number and percentage of subjects who completed or discontinued treatment, primary reason for discontinuation of treatment assigned to one of the reasons listed below
 - Adverse Event
 - Pregnancy
 - o Study Terminated by Sponsor
 - o Death
 - o Withdrawal of Consent to Treatment
 - o Other
- Number and percentage of subjects who completed or discontinued the study, primary reason for study discontinuation assigned to one of the reasons listed below
 - Completed Protocol
 - Adverse Event
 - o Withdrawal of Consent to Study
 - o Death
 - Lost To Follow-Up
 - Study Terminated by Sponsor
 - o Other

Subjects disposition data will also be presented in data listings.

5.1.2. **Protocol Deviations**

A protocol deviation is any change, divergence, or departure from the study design or procedures defined in the clinical protocol.

Protocol deviations will be classified by the sponsor or designee prior to the final analysis and important protocol deviations will be identified as those deviations from the study protocol that may significantly impact the completeness, accuracy, and/or reliability of the trial data; that may significantly affect a subject's rights, safety, or well-being [ICH E3(R1) Q&As, 2013]. The number and percentage of subjects with an important protocol deviation will be tabulated for the SAF.

Separate listings for protocol deviations will also be presented.

5.1.3. Demography and Baseline Characteristics

Descriptive statistics, including number of subjects (n), mean, SD, median, minimum, and maximum, will be used to summarize the following parameters:

- Age (years)
- Weight (kg) at Baseline
- Height (cm) at Baseline
- Body Mass Index (kg/m²) at Baseline

The following demographic categories will be summarized with the number and percentage of subjects:

- Age Groups (years): 18 to $< 35, \ge 35$ to < 55, and ≥ 55 ; < 65 and ≥ 65
- Gender: Male, Female
- Ethnicity: Hispanic or Latino, Not Hispanic or Latino
- Race: American Indian or Alaska Native, Asian, Black or African American, Native Hawaiian or Other Pacific Islander, White, and Other. The details of Other race will be listed as appropriate.
- Baseline scores of MADRS, CGI-S, and HAMD-17
- Number of years having major depressive disorder (MDD) or TRD
- Prior treatment classes, including antidepressant only, combination of antidepressant with others, and non-antidepressant medication which is used to support treatment of depression.

5.1.4. Medical History

System organ class (SOC) and preferred term (PT) of medical history will be coded with MedDRA Version 25.0 or higher. A subject will be counted only once within one SOC and one PT if the subject reported the same SOC and PT multiple times. The summary will be sorted by the frequency of SOCs and PTs in overall total.

Medical history information collected on "Medical History" CRF page will be listed in subject data listing.

5.1.5. **Prior and Concomitant Medications**

All medications will be coded using WHO Drug Dictionary March 2022.

A medication can be classified as either prior or concomitant medication. Prior medication is defined as any medication taken prior to the date of the first study treatment dose. Concomitant medication is defined as any medication taken on or after the date of the first study treatment dose through the end of study.

Prior and concomitant medications will be summarized by Anatomical Therapeutic Chemical (ATC) Classification (2nd level, chemical subgroup [ATC-2]) and preferred name. A subject will only be counted once within each ATC-2 code and within each preferred name. ATC-2 and preferred name will be sorted in descending frequency for the overall number of subjects and then alphabetically for ties.

Prior and concomitant medications will also be presented in data listings.

5.2. Concomitant Procedures

All procedures will be coded using MedDRA Version 25.0 or higher.

Concomitant procedures will also be presented in data listings.

